### Section 3 - Protection and Monitoring Plans (Study 1)

3.1. Protection of Human Subjects [3.1.\\_Protection\\_of\\_Human\\_Subjects20180401.pdf](#)

3.2. Is this a multi-site study that will use the same protocol to conduct non-exempt human subjects research at more than one domestic site?  Yes  No  N/A

If yes, describe the single IRB plan

3.3. Data and Safety Monitoring Plan [3.3.\\_Data\\_and\\_Safety\\_Monitoring\\_Plan\\_draft\\_20180401.pdf](#)

3.4. Will a Data and Safety Monitoring Board be appointed for this study?  Yes  No

3.5. Overall structure of the study team [3.5\\_structure.pdf](#)

### 3. PROTECTION OF HUMAN SUBJECTS

#### 3.1. RISKS TO HUMAN SUBJECTS

**3.1.A. Human Subjects Involvement, Characteristics, and Design.** This proposed Phase II SBIR project will develop a full-scale, fully programmed *B-SMART mobile web app* that aims to enhance the maintenance of behavior change among DWI offenders by mobilizing the DWI offender's social network and enhancing that involvement via smartphone technology. We will complete the development of the *B-SMART mobile web app*, test its usability, translate the complete app to Spanish, and test the impact of the app on alcohol-related outcomes and family function outcomes.

The two target populations consist of first-time DWI offenders and their concerned family members (CFM - defined as a spouse or close relative living with the DWI offender). All participants will be recruited from the Santa Fe County DWI Program, a county-wide program that manages probation and sentencing programs and requirements for all DWI offenders in Santa Fe County, New Mexico.

Inclusion criteria for DWI offenders are: (a) over 21 years of age; (b) first-time offender with an Ignition Interlock Device (IID) installed in their vehicle, (c) have a smartphone, tablet computer, or personal computer with internet access, (d) able to read and speak in English or Spanish, and (e) consent to participate. Inclusion criteria for CFMs are: (a) over 21 years of age; (b) parent, spouse, or immediate family member of a participating DWI offender, (c) have a smartphone, tablet computer, or personal computer with internet access, (d) able to read and speak in English or Spanish, and (e) consent to participate. Participants in the development phase will not be eligible for the randomized trial phase of the project.

The collaborating site is the University of New Mexico (FWA No. 00003255).

#### 3.1.B. **Study Procedures, Materials, and Potential Risks.**

##### **Study Procedures:**

Focus Groups Participants (n=32). Four focus groups will be conducted. Two focus groups will be held with DWI offenders (one in English and one in Spanish). In addition, two focus groups with CFMs will be held (one in English and one in Spanish). Although the app is designed for CFMs, input from DWI offenders will be crucial to learn what they believe would be helpful for them. Focus group discussions will be led by English and Spanish speaking research staff trained in focus group facilitation techniques who will follow a protocol to lead discussions about the use of B-FIT content in smartphone applications. Topics include: how the CFM would share information with the DWI offender; what type of content the DWI offender would expect to see; examples of positive shared activities; and examples of how CFMs can be most supportive of the offender to reduce reoffending.

Discussions will be audio taped, transcribed and analyzed using procedures developed in previous work by the research team. Analysis of all focus group discussions will be accomplished via InVivo NUDIST content and theme analysis software to identify consistent and recurrent content themes in response to focus group questions. These results will be summarized in focus group results reports distributed to research team members and the EAB. These results will be used to make final decisions about smartphone application design, structure, navigability, and approach.

Usability Testing Participants (n=32). One round of iterative usability testing will be conducted with CFMs on an individual basis to validate the design approach and identify usability problems. During individual in-person sessions with research staff, participants will be instructed to navigate through sections of the app and provide their verbal reactions as they do so. Staff will prompt with questions, asking what the participants might change about activities and how they might use the app with their DWI offender. At the completion of the usability session, participants will complete the Bangor System Usability Scale (SUS). In addition to the SUS measure, the Instructional Designer at KB will create a summary report listing usability problems experienced and their severity. The research team and KB media developers will make necessary changes to address these problems before launch in the RCT. All usability sessions will be video recorded and transcribed. Both qualitative and quantitative (Bangor scale) summaries will be provided to Investigators and the EAB for review. All usability testing sessions will be held in New Mexico and will last approximately one hour. Spanish and English speakers will both be recruited.

Randomized Controlled Trial Participants (n=300). First-time DWI offenders and their CFM will be randomized to the intervention (*B-SMART mobile web app*) (n=150) or a usual and customary (UC) IID Information condition comparison group (n=150) following the baseline assessment. Assessments, conducted via web-based surveys, will be conducted with first-time the DWI offenders and CFMs at baseline, 3-month follow-up, and 9-month follow-up post randomization. Also, information on frequency of alcohol-positive IID tests (termed "lockout events") will be acquired by the project from the Santa Fe County and Municipal DWI Program at the 9-month assessment point (posttest only) for each DWI offender. Baseline and follow-up data collection will be conducted via online surveys and a customized web portal and include DWI offender and CFM alcohol frequency and use measures, and measures of family communication and functioning. Participants will fill out a locator form with contact information and collateral contact information to locate them for assessment at the 3-month and 9-month follow-ups.

**Study Materials:** Data from the focus groups, usability testing, surveys, and randomized trial will be collected in the form of handwritten notes, audio tapes, computer files, transcriptions, and questionnaires. Discussions will be recorded, transcribed, and analyzed using *Atlas.ti*® software. Data will be gathered from surveys used in the randomized trial. Data will be obtained specifically for research purposes and will be kept confidential with access limited to the Investigators and specific project staff. All data will be kept in locked files.

**Potential Risks:** Potential risks are minimal, mainly social or psychological. Focus group participants may be hesitant or uncomfortable responding to questions about the challenges of having an IID, concerns about family members' feelings about the IID, and ways that family members could be helpful in supporting the DWI offender to not drink and drive. Usability test participants may not feel comfortable responding to questions about their opinions on appeal, ease of understanding, navigation, and functionality of the *B-SMART* mobile app. There are no anticipated risks from completing the self-report questionnaires. If signs of minor stress or fatigue are apparent, participants will be given time to take a break from completing the questionnaires. For the randomized trial, surveys will be completed online, at the participants own pace.

Participants' responses will not be shared with anyone except project staff. Responses to survey questions will be coded to protect confidentiality. All participants will be allowed to withdraw at any time if they are uncomfortable with the discussions. Although half of the potential participants are involved with the criminal justice system as a result of having a DWI, that involvement is overseen by other entities and is not a part of the research project.

### **3.2. ADEQUACY OF PROTECTION AGAINST RISKS**

#### **3.2.A. Informed Consent and Assent.**

Human Subjects oversight will be conducted by the Western Institutional Review Board (WIRB; DHHS IRB Reg. No. IRBooooo53; FWA No. 00003715) and the University of New Mexico's Institutional Review Board (DHHS IRB Reg. No. IRBoooo431; FWA No. 00004690). All consenting procedures will be IRB-approved. The IRB(s) will review and approve subject materials (including recruitment letters, consent forms, survey instruments) and data management procedures prior to study implementation. Potential participants will be informed of the study purposes and procedures, given opportunities to ask questions and have them answered, and provide informed consent according to IRB-approved guidelines.

Focus group and usability test participants will be consented in-person and will sign an IRB-approved consent form. For the randomized trial, DWI offenders recruited to the study will be consented in-person and will be administered by a UNM Project Coordinator. Project staff will provide participants with copies of their signed IRB-approved consent forms. For the randomized trial, CFMs will be consented online and will have an option to save or print the IRB-approved consent. Participants will only be enrolled in the trial if both the DWI offender and CFM consent to participate. Consent forms will be either Spanish or English, dependent on the participants' language.

The IRB-approved consent forms will describe the purpose of the project, risks and benefits, and selection criteria. Participation will be voluntary, with the right to stop participating at any time. No clinical data will be captured. All data coding, data entry, analysis, and reporting activities will be conducted by KB. Participants will be informed that they have a right to withdraw from the study at any time. No additional data will be collected from participants who decide to withdraw; however, the information collected prior to withdrawal will remain in the study. IRB-approved surveys and discussions will be carried out under the supervision of senior project staff.

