### 3C.6. Randomized Trial Evaluating *B-SMART* (Specific Aim 4; Months 8-24)

**3C.6.1. Experimental Design.** The *B-SMART mobile web app* will be evaluated in a randomized pretest-posttest controlled design. In months 6-11, first time DWI offenders and CFMs will be recruited for participation in the trial. First-time DWI offenders and their CFMs will be randomized together to the intervention (*B-SMART*)

(n=150) or a usual and customary (UC) IID information condition comparison group (n=150) following baseline assessment. Assessment via web-based surveys will be conducted with the DWI offenders and CFMs at baseline, 3-month follow-up, and 9-month follow-up

post randomization. Also, information on frequency of alcohol-positive IID tests (termed “lockout events”) will be acquired by the project from the Santa Fe County and Municipal DWI Program at the 9-month assessment point (posttest only) for each DWI offender. Thus, the proposed efficacy trial (see **Figure 5**) will be a 2 (level of treatment – app intervention vs. UC information) x 3 (level of time – baseline vs. 3-month follow-up vs. 9-month follow-up) mixed factorial design. Baseline and follow-up data collection will be conducted via online surveys and a customized web portal and include DWI offender and CFM alcohol frequency and use measures and measures of family communication and functioning (see 3C.7). Participants will fill out a locator form with contact information and collateral contact information to locate them for assessment at the 3-month and 9-month follow-ups. We have employed these locator procedures in prior trials, keeping average loss across 9 months at 15%-20%. Cumulative IID lockout event data will be collected for all DWI offenders from the Santa Fe County DWI Program at the 9-month assessment point.

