## 3C.7. Outcome Measures

**3C.7.1. Measure of Primary Outcome Variable: IID Lockout Events.** The primary outcome

measure will be frequency of IID lockout events from baseline to 9-month follow-up post-randomization, collected from the Santa Fe DWI program database for each first-time DWI offender participant. Marques, Voas and colleagues have demonstrated in a series of investigations that frequency of lockout events strongly predicts DWI recidivism over time, and as such, IID lockout events are an important and useful proxy measure for DWI recidivism. Given the length of time necessary to accumulate DWI recidivism data (average length of time varies across locales and can be between 2 and 8 years), IID lockout events provide a direct and accessible measure of DWI recidivism within the two-year project timeline.

**3C.7.2. Measures of Secondary Outcome Variables and Mediators.** Alcohol use by the DWI offender, a secondary outcome, will be assessed at baseline, 3-month follow-up, and 9-month follow-up with versions of the Form 90 adapted for online assessment for the CFMs (Form 90-ACS) and first-time DWI offenders (Form 90-AF). The Form 90 measures produce detailed quantity and frequency measure of alcohol use for the first-time offender that are validated by the CFM reports. Family functioning will be assessed at baseline, 3-month follow-up, and 9-month follow-up, as potential mediators of *B-SMART* effects, with DWI offenders and CFMs with three measures: (1) Family Environment Scale – Cohesion and Conflict subscales assesses offender and CFM perceptions of positive and negative family functioning; the two subscales selected are strongly associated with treatment outcome; (2) Family Communication Scale from FACES-IV assesses perception of quality of communication in the family; (3) Pleasant Events Schedule (adapted) assesses shared positive activities within a family. These three measures are also being used in the B-FIT study, allowing for comparison of outcomes across the two studies.

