**Planned Analysis for Hypothesis 1.** The second major analysis will focus on impact of the *B-SMART mobile web app* on primary (IID lockout events) and secondary (DWI offender's alcohol consumption) outcomes and be completed within 1 month of the end of the posttest data collection in Year 2. The effect of *B-SMART* on IID lockout events in Hypothesis 1 will be tested primarily using PROC GENMOD with a Poisson link via SAS Version 9.4, which includes capabilities to test these Poisson models with missing data, account for the temporal design, and include information by participant. Participants will be treated as a random effect and treatment as a fixed effect, at  $p=0.05$  (2-sided). Analyses of primary outcomes will not be released before completion of the intervention. Since CFM and DWI offender can be clustered within the same family, hierarchical models with participants nested within families will be considered.

The secondary outcome of quantity and frequency of alcohol consumption by DWI offenders will be compared in several ways. Quantity and frequency will be evaluated using Poisson models, as well as a composite variable based on total alcohol consumption (the product of the two variables), using negative binomial regression models, unless a Poisson model is sufficient.

Since date of IID lockout events will be collected and alcohol consumption is measured at all three assessments, we will examine the time by treatment interaction in the analyses of Hypothesis 1 to assess the

question of the durability of the effects of B-SMART over time. For example, we will evaluate time to first lockout using a Kaplan Meier approach and the times to subsequent lockouts.

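### Read plainly, the withdrawal rule combined with a single month-9 records request leaves an offender who formally withdraws early with no primary outcome, and it conflicts with the promise of lockout data for all offenders.

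*Combined protocol and SAP*

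**What the plan says.** The withdrawal rule is in section 3.2.A (Informed Consent and Assent): "No additional data will be collected from participants who decide to withdraw". The same sentence adds that "the information collected prior to withdrawal will remain in the study". Program records are not mentioned as an exception.

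The primary outcome (3C.7.1) is the "frequency of IID lockout events from baseline to 9-month follow-up post-randomization", taken from the county DWI program's database. Sections 3C.6.1 and 3.1.B both place its acquisition at one time, "at the 9-month assessment point (posttest only) for each DWI offender". The study-team structure repeats the month-9 plan for the data collection committee. No earlier request is described.

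Section 3C.6.1 also states: "Cumulative IID lockout event data will be collected for all DWI offenders from the Santa Fe County DWI Program at the 9-month assessment point". It does not say whether this includes offenders who have withdrawn.

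Two analysis statements bear on the point, both in 3C.8.2 and in the SAP under Planned Analysis for Hypothesis 1. The records carry event dates ("Since date of IID lockout events will be collected"). On missing data, the plan says only what the software can do: "which includes capabilities to test these Poisson models with missing data".

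**The concern.** The primary outcome is an administrative record that needs no contact with the participant, so it could be close to complete whatever happens to the surveys. The withdrawal rule ties its completeness to willingness to stay in the study. Because the only request is at month 9, nothing has been collected when someone withdraws in, say, month 2, and on the plain reading nothing may be collected afterwards. Dated events from the months of consented participation are lost as well.

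With one count per person, a withdrawer has no partial count to model, so a Poisson regression simply omits that person. If withdrawal relates to drinking and differs by arm, the primary rate ratio is biased, and a larger sample does not remove this.

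**Working it through.** **1. The passages side by side.** Retained after withdrawal: what was already collected (3.2.A). Collected before month 9: no lockout data (3C.6.1, 3.1.B). Collected after withdrawal: nothing (3.2.A). On the plain reading, an offender who withdraws before month 9 has no primary outcome. Section 3C.6.1 nevertheless covers all offenders, and both statements cannot be followed literally once someone withdraws.

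**2. The plan's own sample size.** Inputs from 3C.6.5 and the SAP: 4 lockouts over 9 months in control, two-sided 0.05, 90% power, about a 20% reduction, 15% attrition, 150 offenders per arm. Wald test on the log rate ratio:

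n per arm = (z₀.₉₇₅ + z₀.₉₀)² × (1/m₁ + 1/m₂) / [ln(m₂/m₁)]²

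- 4 vs 2.4: 10.507 × 0.6667 / 0.2609 = 26.8, so 27 as stated.
- 4 vs 3.2: 10.507 × 0.5625 / 0.04979 = 118.7, so 119 as stated.

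**3. Precision at the ceiling.** Assume that all of the 15% attrition is formal withdrawal, leaving 150 × 0.85 = 127.5 per arm. Power = Φ(|ln 0.8| / √(0.5625/n) − 1.96).

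- n = 150: Φ(0.2231/0.06124 − 1.96) = Φ(1.68) = 95.4%.
- n = 127.5: Φ(0.2231/0.06642 − 1.96) = Φ(1.40) = 91.9%.

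These figures use an exact 20% reduction, which is what 119 corresponds to. For the printed rates 0.44 and 0.36 (ratio 0.818), power is 90.7% with 150 per arm and 85.5% with 127.

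**4. What the lost months are worth at the same ceiling.** Assume that withdrawals are spread evenly, so 4.5 months each on average. Then 45 offenders × 4.5 = 202.5 person-months before withdrawal are discarded, about 90 lockouts at the control rate (202.5 × 4/9). Keeping them gives an effective 127.5 + 22.5 × 0.5 = 138.75 per arm and power of 93.9% for 4 vs 3.2.

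**5. Bias with no true effect.** Let a fraction w of an arm withdraw, with h times the lockout rate of those who stay, and the same overall mean in both arms. The observed arm mean is then proportional to 1/(1 − w + wh), and

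observed ratio (app/control) = (1 − w_c + w_c·h) / (1 − w_a + w_a·h)

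The documents give neither w nor h; all of the values below are assumptions.

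| Withdrawal, app vs control | h = 1.5 | h = 2 |
|---|---|---|
| Equal | 1.00 | 1.00 |
| 6% vs 3% | 1.015/1.03 = 0.985 | 1.03/1.06 = 0.972 |
| 20% vs 10% | 1.05/1.10 = 0.95 | 1.10/1.20 = 0.92 |
| 10% vs 20% | 1.10/1.05 = 1.05 | 1.20/1.10 = 1.09 |

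As a share of the planned effect (ln 0.8), 6% vs 3% gives 7%-13% and 20% vs 10% gives 21%-39%, both in favour of the app. With the arms reversed, the bias runs against the app.

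**The case against.** The strongest counter-argument is textual. The rule concerns data collected from participants, whereas lockouts come from the county program. Section 3.2.B, in the same human-subjects part, describes the project's data as tests, survey questions and interviews. On that reading, withdrawal ends surveys and contact, the month-9 request goes ahead for everyone, and there is no conflict. This reading is possible, but nothing in the text adopts it, and staff and the IRBs would have to choose. The consent form is not in the public file and may already settle the matter. That would not remove the need for the protocol to agree with it.

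Several stronger conclusions are tempting but not supported:

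- **That the primary outcome will suffer the 15%-20% survey loss.** Those figures describe general loss to follow-up. The retention plan treats persistent non-responders separately from people who withdraw, and records can still be requested for offenders who only stop answering. Formal withdrawal could be far below 15%.
- **That the trial becomes underpowered.** For a true 20% reduction, power stays above 90% even at the ceiling, because the sample size already allows for 15% loss. The shortfall for 0.44 vs 0.36 in step 3 comes mainly from a separate mismatch: that pair needs about 147 per arm, not 119.
- **That the result will favour the app.** The documents do not predict the direction. Reminders every 5 days for two weeks and follow-up calls go to both arms (3C.6.3). The app is at most 120 minutes and can be left unused without withdrawing. Differential withdrawal is possible but not shown.

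**Conclusion.** The point holds in a limited form. On the plain reading, formal withdrawal before month 9 removes an offender's whole primary outcome, including months already consented to, and this conflicts with the commitment to collect lockouts for all offenders. Because a narrower reading exists, the defect is an unresolved inconsistency with a real consequence, rather than a certain loss of data.

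The effect on precision is modest: at most 95.4% down to 91.9% for 4 vs 3.2 under the Poisson assumption, and less if withdrawal is below 15%. The effect on validity cannot be sized from the documents. It is zero if withdrawal is equal across arms under the working model, or if withdrawal is unrelated to lockout rate. Otherwise, under the assumed inputs, it runs from 0.985-0.972 (6% vs 3%) to 0.95-0.92 (20% vs 10%), with 1.05-1.09 if the arms are reversed. The 20% vs 10% case is an illustration, not a forecast. A change is justified because the exposure is avoidable at low cost and the plan names no method for missing primary counts.

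**What to change.** In section 3.2.A and the consent form, define two separate choices:

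- **(a) Stopping surveys, contact or app use.** Consented retrieval of IID records through month 9 continues.
- **(b) Revoking records access.** The consent states in advance whether lockouts dated before revocation may be retrieved. If so, they are counted to the revocation date, with log(observed time) as an offset in the primary model. If not, the count is missing and reported as such.

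Amend 3C.6.1 so that the reference to all offenders matches these choices. State what happens to the offender's records if only the family member withdraws, which the documents leave open. Report withdrawals of each type by arm, and name a sensitivity analysis for missing counts.

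A routine extra extract at month 3 is unnecessary. It would not help someone who withdraws in month 2, and the dated month-9 extract can be cut off at the revocation date.

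The cost is protocol and consent wording, IRB review, and a date cut-off in the existing month-9 extract for those who revoke. The human-subjects form lists the trial as not yet recruiting. Anyone already enrolled under the present wording would need the IRB's view on whether the new terms can apply.
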